## 7. SAMPLE SIZE CONSIDERATIONS

Analysis of covariance with clinical site and baseline cue as the covariates will be used to model the primary outcome – the VAS craving score for the alcohol cue. Statistical power was estimated using [PASS 13] with the following parameters. The treatment effect parameter—a maximal 3-point study drug-placebo difference on the strength of VAS craving in response to the alcohol cue—was obtained from [Roberts \(2017\)](#), which used a similar cue reactivity paradigm. The mean values on this outcome at Week 3 are assumed to be 11 for ASP8062 and 14 for placebo and a standard deviation between subjects of 4. Clinical site and the baseline VAS craving for the alcohol cue were assumed to have correlations of 0.13 and 0.39, respectively, with the primary outcome. These correlations, coupled with assumed standard deviations for site and baseline VAS craving for the alcohol cue of 0.82 and 4, respectively, yield explained variation of 26%. These assumptions, with a sample size of 30 subjects per arm (60 total subjects), provides 87% statistical power with a 0.05 two-sided significance level.

## **8. DATA QUALITY ASSURANCE**

Data quality assurance will start with training of clinical investigative staff on data collection and assessment procedures including a Manual of Operations that describes what data to collect and procedures for completion of eCRFs. Completed eCRFs will be reviewed by Fast-Track Drugs and Biologics clinical monitors on a regular basis throughout the trial by comparison against the source documents.

Study data will come from the eCRFs, TLFB spreadsheets, coded AEs, coded medical history, AiCure Drug Compliance system outputs, and PK drug levels from the PK lab spreadsheets. eCRFs for this study were created using an electronic data management system (EDMS) based on IBM clinical development system. eCRFs were created using an established data dictionary for each variable including the field name, field type, field attributes, and coding for variables. Range checks, alpha-numeric requirements, and null/not null parameters were programmed as applicable. The back end database application is Oracle. Data entered into the EDMS system will be reviewed by Fast-Track clinical monitors and data managers. If incomplete or inaccurate data are found, the data will be queried in the system for site staff to address. The site will resolve data inconsistencies and errors using the EDMS with full audit trail of corrections being maintained within the system. Corrections and changes to the data will be reviewed by Fast-Track clinical monitors and data managers. TLFB spreadsheets have a double data entry check system and additionally, Fast-Track staff will verify the data entries with the drinking calandar to verify the correct percentages of alcohol by volume. QA review of laboratory data outputs is the responsibility of the individual testing laboratories; however, Fast-Track staff will verify that there is a result reported for each specimen that was recorded in the database as being collected. Coded AEs and medical history terms will be cross checked by a second trained MedDRA coder.

Additional edit checks will be written to detect anomalies in the database. These checks will address inconsistencies (within visits, across visits), invalid/unusual values, missing values, and protocol violations. Edit checking will be validated on test data or actual clinical trial data. In addition to programmed edit checks, quality control examination of data will also be performed on reviews of data listings.

## **9. STATISTICAL CONSIDERATIONS**

### **9.1. General Considerations**

For descriptive purposes, dichotomous and categorical variables will be presented as number of observations and percentages; continuous variables will be given as means, standard deviations (SD), median, minimum (min) and maximum(max). Statistical tests will be two-tailed at a 0.05 Type I error rate. P-values for the primary and secondary endpoints of  $< 0.05$  will be considered statistically significant. Endpoint data will also be screened for outliers and skewness.

Appropriate non-parametric tests will be used to compare treatment groups on continuous baseline characteristics that are not normally distributed. Continuous endpoint data that are not normally distributed will be transformed using either a square root, logarithmic, or inverse transformation, the selection of which is determined by skewness and kurtosis statistics with values closest to zero. Cohen's d will be used to calculate the effect size for means and Cohen's h or odds ratios will be used to calculate the effect size for proportions. Descriptive statistics – mean, SD, median, min and max – of all endpoint data will be provided for each assessment point or summarized at each week for drinking endpoints. All data will be presented in listings.

### **9.2. Participant Accountability and Protocol Deviations**

A summary will be prepared to show dropouts/retention over time in each group, along with the reason for early discontinuation. The number of missing observations will be presented between groups. Protocol deviations will be presented as summaries by type of deviation.

### **9.3. Demographics and Other Baseline Characteristics**

Summaries of the characteristics of the subjects in each of the study groups at baseline will be prepared for the mITT, and evaluable analysis sets. Demographic characteristics (e.g., age, gender, race, and ethnicity) and other baseline characteristics, coded medical history terms, screening cue session VAS scale scores and ACQ-SF-R pre and post session score, mood scales (e.g., POMS total and subscale scores), Hyperkatifeia Scale scores, PSQI, and drinking goal, MINI AUD scores and other DSM-5 diagnoses will be summarized by treatment group for the mITT and evaluable subjects. Chi-square tests or t-tests will be used on baseline characteristics to test the hypothesis of effective randomization. Imbalance in any of these factors is an indication of ineffective randomization which may bias the results observed on any of the endpoints.

Baseline drinking parameters in the 28-days prior to the start of screening, will be summarized by treatment group for the mITT subjects. t-tests will be used for baseline drinking parameters to test the hypothesis of effective randomization. The number and percentage of subjects with mild, moderate and severe symptoms of AUD and summary statistics for total number of symptoms will also be presented.

The quantity of cigarettes smoked per week in the week prior to randomization will be presented for those subjects who reported any smoking. The numbers and percentages of subjects who report other nicotine product use at baseline, any nicotine use, and who test positive for THC will also be presented. Because smoking, any nicotine use, and positive THC are subsets and are not

controlled by randomization, balance across treatment groups will be assessed using t-test and chi-square tests.

Baseline drinking-associated consequences (CIWA-AR and PROMIS Alcohol Negative Consequences scores) and drinking-associated-craving (PACS) total score and subscales will be summarized in the tables. t-test will be used to test for balance across the treatment groups and evaluate the hypothesis of ineffective randomization.

Continuous variables will be summarized using means, standard deviations, medians, minimum, and maximum values. Categorical variables will be summarized using counts and percentages.

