Continuous secondary endpoints (percent heavy drinking days, percent very heavy drinking days, percent days abstinent, drinks per week, drinks per drinking day, number of cigarettes smoked per week, PACS, POMS, and PSQI score) during the last 4 weeks of treatment period will be analyzed using a mixed-effects model with site, assessment time, and baseline drinking as fixed factors. PROMIS will be analyzed with analysis of covariance model with baseline and treatment as factors. Models will also include time by treatment group interaction term. Additional covariates may be included that are significantly correlated with outcome and/or if there are differences across the treatment groups.

Analysis of the dichotomous secondary endpoints (percentage subjects with no heavy drinking days, percentage subjects abstinent from alcohol, percentage of subjects achieving at least a one and two-level shift in WHO alcohol consumption, and percentage of subjects with no nicotine use among subjects with any use during the week before randomization) during the last 4 weeks of treatment period will be conducted via logistic regression. Covariates may be included provided there are a sufficient number of events.

No imputation for missing endpoint data will be performed for secondary endpoints.

Safety Analyses: AEs will be coded using the most recent version of the Medical Dictionary of Regulatory Activities (MedDRA) preferred terms and will be grouped by system, organ, and class (SOC) designation. The severity, frequency, and relationship of AEs to investigational product will be presented by preferred term by SOC grouping. Listings of each individual AE including start date, stop date, severity, relationship, outcome, and duration will be provided. Each AE (based on preferred terminology) will be counted once only for a given

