### **12.1.2. Demographic and Baseline Characteristics**

**Table 16: Demographic Characteristics - mITT Subjects**

Characteristic	ASP8062	Placebo	Total	p-value 
Age (years)				0.xxx
N	xx	xx	xx	
Mean	xx.x	xx.x	xx.x	
SD 	xxx.xx	xxx.xx	xxx.xx	
Median	xx	xx	xx	
Min-Max	(xx-xx)	(xx-xx)	(xx-xx)	
Gender				0.xxx
N				
Male	xx (xx.x%)	xx (xx.x%)	xx (xx.x%)	
Female	xx (xx.x%)	xx (xx.x%)	xx (xx.x%)	
Race				0.xxx
N	xx	xx	xx	
White	xx (xx.x%)	xx (xx.x%)	xx (xx.x%)	
African-American or Black	xx (xx.x%)	xx (xx.x%)	xx (xx.x%)	
Asian	xx (xx.x%)	xx (xx.x%)	xx (xx.x%)	
Native Hawaiian or Other Pacific Islander	xx (xx.x%)	xx (xx.x%)	xx (xx.x%)	
American Indian or Alaskan Native	xx (xx.x%)	xx (xx.x%)	xx (xx.x%)	
Other	xx (xx.x%)	xx (xx.x%)	xx (xx.x%)	
Ethnicity				0.xxx
N	xx	xx	xx	
Hispanic or Latino	xx (xx.x%)	xx (xx.x%)	xx (xx.x%)	
Not Hispanic or Latino	xx (xx.x%)	xx (xx.x%)	xx (xx.x%)	

c = chi-squared test, f=Fisher's exact test, w=Wilcoxon signed rank test SD is standard deviation**Table 17: Demographic Characteristics – Evaluable Subjects**

Same as Table 16

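### SAP 9.3 reads any baseline imbalance as a sign of ineffective randomization, an inference that does not follow and is likely to raise a false alarm

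*SAP*

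**What the plan says.** SAP 9.3 states the purpose of the baseline tests: "Chi-square tests or t-tests will be used on baseline characteristics to test the hypothesis of effective randomization". It then gives the reading of a difference: "Imbalance in any of these factors is an indication of ineffective randomization which may bias the results observed on any of the endpoints". The same purpose is repeated for the drinking history ("t-tests will be used for baseline drinking parameters to test the hypothesis of effective randomization") and for CIWA-AR, PROMIS and PACS ("t-test will be used to test for balance across the treatment groups and evaluate the hypothesis of ineffective randomization"). Smoking, nicotine use and THC are also tested for balance, but 9.3 describes them as subsets that randomization does not control.

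The only significance level is in SAP 9.1: "Statistical tests will be two-tailed at a 0.05 Type I error rate". No other threshold for imbalance is given, and no multiplicity control is stated for these tests. SAP 9.1 also provides for non-parametric comparison of baseline variables that are not normally distributed.

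The summaries are for the mITT and evaluable sets. SAP section 4 defines mITT by at least one dose and a non-missing primary VAS score, and evaluable by tablets taken on at least 80% of days in Weeks 1-6.

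The protocol (Statistical Methods, Baseline Descriptive Statistics) says the groups will be compared at baseline by suitable methods, and names the mITT, evaluable and safety sets. Under Analysis of the Secondary Endpoints it allows extra covariates that correlate with outcome and/or "if there are differences across the treatment groups".

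**The concern.** Allocation is by permuted blocks stratified by site. If it is carried out as planned, every baseline difference among randomized subjects is chance, and a small p-value says nothing about whether randomization worked. In the mITT and evaluable sets a difference has a second possible source: who stayed to Week 3, or who took the tablets. In neither case does the conclusion in 9.3 follow. No baseline shell covers all randomized subjects, which is the only group in which allocation itself could be examined.

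Two things are at stake. First, a study report that follows 9.3 would describe a sound randomization as apparently ineffective and the endpoint results as possibly biased. Second, the protocol clause on group differences would let imbalance influence the covariates of the secondary models. Seeing a group difference requires treatment labels, whereas SAP 9.4.4 selects covariates before unblinding, on data pooled over arms. The two rules conflict.

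**Working it through.** The documents give no false-alarm rate, so there is no figure to reproduce. The check is a count of tests followed by the chance of at least one false positive when randomization is sound.

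**Inputs.** The level is 0.05 two-sided (SAP 9.1). The count is of p-value cells in the mITT shells of SAP 12.1.2:

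| Group in SAP 9.3 | Shells | Cells |
|---|---|---|
| Paragraph containing the imbalance rule | Table 16 (4), Table 18 (15), Table 22 (7), Table 24 (1), Table 26 (5), Table 30 ACQ-SF-R rows (2) and Hyperkatifeia rows (5) | 39 |
| Baseline drinking | Table 28 | 10 |
| CIWA-AR score, CIWA-AR of 10 or more, PROMIS, PACS | Table 30, remaining rows | 4 |
| Smoking, nicotine, THC (balance only) | Table 32 | 6 |

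The tests framed as randomization checks number 39 + 10 + 4 = 53. All cells number 53 + 6 = 59. The evaluable-set shells repeat them.

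**Independent tests.** Expected false positives = 0.05k, and P(at least one) = 1 - 0.95^k.

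- k = 39: 0.05 × 39 = 1.95 expected; 1 - 0.95^39 = 86.5%.
- k = 53: 0.05 × 53 = 2.65 expected; 1 - 0.95^53 = 93.4%.
- k = 59: 0.05 × 59 = 2.95 expected; 1 - 0.95^59 = 95.2%.

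**Correlated tests.** The documents give no correlations, so these values are assumptions. For test statistics that are standard normal with common correlation ρ,

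P(at least one) = 1 - ∫ [Φ((1.96 - √ρ x)/√(1-ρ)) - Φ((-1.96 - √ρ x)/√(1-ρ))]^k φ(x) dx.

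| k | ρ = 0 | ρ = 0.3 | ρ = 0.5 |
|---|---|---|---|
| 39 | 86.5% | 74% | 57% |
| 59 | 95% | 85% | 66% |

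A single common correlation is a crude model. A simulation of all 59 tests at 30 per arm built averages, totals and differences from their items, with correlation only within blocks of related measures (0 to 0.85 assumed). It gave about 82% to 91%. Correlation leaves the expected number of false positives essentially unchanged (about 2.9 in that simulation) but clusters them in fewer trials.

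**Route into the models.** Three places need to be read together.

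- SAP 9.4.1 fixes the primary ANCOVA terms: treatment, site and pretreatment score. SAP 9.4.2 analyses the confirmatory endpoints in the same way. Baseline imbalance cannot enter either.
- SAP 9.4.4 chooses extra secondary covariates blinded, by correlation with outcome of at least 0.20 and by clinical expertise. Imbalance is not a criterion.
- The protocol permits imbalance as a criterion for the secondary models. This is the only route by which a chance difference could change a model.

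**A shell error.** The Table 16 footnote lists "w=Wilcoxon signed rank test". That is a paired test, and the two arms are independent groups.

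**The case against.** The strongest reply is that 9.3 has no operative effect. It calls imbalance only an indication, says results may be biased, sets no explicit cut-off, attaches no action and prescribes no sentence for the report. No model in the SAP depends on it. The protocol clause is permissive, applies only to secondary endpoints and is not tied to the 9.3 p-values, and the SAP's blinded rule already settles the matter in the preferred direction. On this view, removing baseline p-values is largely a reporting preference.

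Much of this stands, and it rules out several stronger readings that a reader might infer:

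- That a false alarm is almost sure across 59 tests. The imbalance sentence refers to the factors of its own paragraph, which have 39 cells. Six of the 59 are expressly not randomization tests. The tests also overlap heavily: VAS items with their averages and differences, POMS total with its subscales, and 28-day with 7-day drinking.
- That the SAP would declare randomization failed. Its word is ineffective, and it is hedged.
- That the primary result is in danger. Its model terms are fixed.
- That imbalance decides covariates. The protocol only permits this, and the SAP does not adopt it.

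What the reply does not answer is that the stated inference is wrong, is framed as a test of randomization in three places, and is applied to sets that cannot isolate randomization. Examining mITT or evaluable subjects for differential exclusion is reasonable as description, but 9.3 interprets the result as something else.

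**Conclusion.** The point holds and should be fixed, although it does not threaten the primary analysis. SAP 9.3 states a wrong inference. If allocation is executed soundly and imbalance is judged at the only level given (0.05), at least one false alarm among the 39 cells covered by the rule has a probability of 86.5% under independence, and 74% or 57% at assumed common correlations of 0.3 or 0.5. Over the 53 cells framed as randomization checks it is 93.4% under independence, which is an upper figure given the overlap. A false alarm is likely, not certain. The harm is limited to the report's statement about randomization and to the protocol's opening for unblinded, imbalance-driven covariates in the secondary models. No sample size or power figure changes.

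**What to change.** 1. Remove the randomization-hypothesis wording from every paragraph of SAP 9.3 where it appears, including those on baseline drinking and on CIWA-AR, PROMIS and PACS. State that the baseline tables are descriptive.
2. Drop the p-value columns wherever they occur in Tables 16-33, together with the matching test text in 9.3 (including smoking, nicotine and THC) and the baseline non-parametric tests in 9.1. Align the protocol's Baseline Descriptive Statistics paragraph. Add a baseline summary for all randomized subjects, with standardised differences if wanted.
3. Delete the protocol clause "if there are differences across the treatment groups" and its connecting and/or, so that extra covariates follow only the blinded rule in SAP 9.4.4.
4. If any baseline test is kept, change the Table 16 footnote from the signed-rank to the rank-sum test.

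The cost is wording changes to the SAP, shells and protocol. Programming falls, apart from the one added summary.

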## **9.4. Efficacy Analysis**

### **9.4.1. Primary Analysis of the Primary Efficacy Endpoint**

Each subject will have an initial alcohol cue for “strength” of craving score from the VAS that is the primary endpoint. Analysis of covariance (ANCOVA) with the ”strength” of alcohol craving value as the dependent variable and the pretreatment “strength” of alcohol craving score from the alcohol cue as an independent fixed effect. Treatment and clinical site will also be included as independent factors.

No imputation for missing endpoint data will be performed.

### **9.4.2. Confirmatory Secondary Endpoints**

There are 3 additional VAS craving questions and a beverage liking question asked during the human lab session. Each of these questions will be analyzed in the same manner as listed in Section 9.4.1. An overall mean of the 4 VAS craving items will also be analyzed similarly for just the alcohol beverage cue. The difference between the alcohol cue and water cue for each VAS item will be computed at both the pre and post treatment time points. The difference values for each VAS item and the average difference will be analyzed similarly to the primary endpoint.

### **9.4.3. Analysis of the Secondary Efficacy Endpoints**

Secondary efficacy endpoints will also be analyzed based on data collected during the last 4 weeks of the maintenance period (Weeks 3 through 6), including TLFB and other questionnaire data assessed at Week 7 that reflect data collected during this period. Note that the data collected at Week 7 reflect drinking and other questionnaire items that occurred during Week 6.

In general, every continuous secondary efficacy endpoint is analyzed using a repeated measures mixed effects model where subjects are random effects; factors and covariates are fixed effects. The analyses will be performed using SAS PROC MIXED procedure. The information criterion is requested from every mixed effects model. Subjects are treated as a class variable and not continuous. The week (Weeks 3 through 6), treatment group, and clinical site are also treated as class variables.

The primary analysis model for all continuous endpoints is:

- Appropriately transformed endpoint = treatment + week + treatment\*week + clinical site + baseline equivalent of endpoint + other covariates (identified in Section 9.4.4)

This model will also be created for the untransformed endpoint. The solution statement from SAS PROC MIXED is requested to provide the solution for the fixed effects parameters. A

REPEATED statement specifies that values are repeated each week and subjects are nested within treatment group. The covariance structure is specified.

The selection of the covariance structure is performed using a simple repeated mixed effects model that includes treatment group as the only fixed effect and subject nested within treatment group as the only random effect. The covariance structure for each continuous secondary endpoint is selected from autoregressive, compound symmetry, Toeplitz, and unstructured. The Akaike Information Criterion (AICc) corrected for a finite sample is obtained from each of the four models for the four possible covariance structures to determine model fit. The smallest (minimum) AICc associated with one of the covariance structures is selected and the difference for each of the other three covariance structures are calculated. A graph is produced of the model fit statistics and relative difference for the four possible covariance structures. The graphs across the continuous endpoints are compared to determine which covariance structure will be selected for all continuous endpoints or if one or more models need different covariance structures.

Results based on the primary analysis model and the model of the untransformed endpoint will be presented in tabular form. The overall least squares means and least square means for each time point along with the 95% confidence intervals (CI) will be presented for the untransformed endpoint only, while two-tailed p-values and Cohen's d will be presented for both the untransformed and transformed data. Inference and Cohen's d will be based upon the results using appropriately transformed data. Graphs of all secondary endpoints will be produced.

#### **9.4.3.1. Secondary Drinking Endpoints**

Percentage of days abstinent per week, percentage of subjects abstinent, percentage of heavy drinking days per week, percentage of very heavy drinking days, weekly mean number of drinks per week, and weekly mean number of drinks per drinking day will be analyzed using the mixed effects model specified in Section 9.4.3. Covariates for these models will be identified as in Section 9.4.4.

Percentage of subjects with a WHO 1-level decrease, and WHO 2-level decrease in alcohol consumption risk category will be analyzed during the last 4 weeks of the maintenance period (Weeks 2 through 5) using a logistic regression model. Covariates for the logistic regression will be identified as in Section 9.4.4. 2x2 contingency tables will report the WHO 1-level decrease, and WHO 2-level decrease along with Cohen's h, odds ratios and 95% CIs. The Wald statistic will be used to test for treatment differences.

No adjustment for multiple comparisons and no imputation will be used for these endpoints.

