### **9.4.4. Covariate Adjustment for the Analysis of Secondary Efficacy Endpoints**

Covariates for continuous secondary efficacy endpoints include the baseline equivalent of the endpoint, clinical site, treatment, time and the treatment by time interaction. Additional covariates for the secondary efficacy endpoints may include baseline characteristics with a theoretical and/or empirical basis for a relationship with a particular secondary endpoint. Such characteristics may include, but are not limited to, drinking goal (stop drinking versus reduce drinking but not stop), age, and baseline alcohol craving scale total score. Prior to the unblinding of the data, matrices of correlations between these baseline characteristics and each of the secondary efficacy endpoints, pooled across blinded treatment assignment, will be produced (using Pearson for continuous variables, Spearman for categorical outcomes). Selection of baseline variables to include as covariates in the models will be based on consideration of the following criteria: at least modest correlation with outcome (i.e.,  $r \geq 0.20$ ) and clinical expertise. Each endpoint may have a unique set of covariates. Care is taken to only select a limited number of covariates such that the models are not over fitted.

Covariates for the dichotomous secondary endpoints, percentage of subjects abstinent, WHO 1-level risk category decrease, and WHO 2-level risk category decrease in alcohol consumption, will use phi correlation with dichotomous variables, chi-square statistic for categorical variables, and biserial correlation. Fewer covariates for the logistic regression may be used depending upon the number of events. If the number of events permits the inclusion of a baseline drinking covariate, the percentage of days abstinent will be used as the covariate for the percent subjects abstinent endpoint and the percent heavy drinking days will be used as the covariate for the percent subjects with no heavy drinking days endpoint; however, no baseline drinking covariate will be employed for the endpoint, percent subjects with a WHO decrease in alcohol consumption, as this endpoint already adjusts for baseline drinking in its calculation.

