**Table 69: Percentage of Subjects Abstinent from Alcohol Weeks 3-6 – Full Model Logistic Regression (mITT)**

Presented in same manner as Table 67 *programming note: baseline PDA is a covariate for PSA outcome*

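### SAP 9.4.3.1 sends the yes/no endpoint of subjects abstinent to the weekly linear mixed model, against the protocol, SAP 9.4.4 and Table 69; its text also leaves out no heavy drinking days

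*SAP*

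**What the plan says.** SAP 9.4.3.1 opens with a list of endpoints that includes "percentage of subjects abstinent, percentage of heavy drinking days per week", together with days abstinent, very heavy drinking days and the two drink-count endpoints, and ends by saying that all of them "will be analyzed using the mixed effects model specified in Section 9.4.3". The next paragraph assigns logistic regression, the Wald test, odds ratios and Cohen's h to the WHO 1-level and 2-level decreases only.

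SAP 9.4.3 limits the mixed model in scope: "every continuous secondary efficacy endpoint is analyzed using a repeated measures mixed effects model where subjects are random effects". It is a PROC MIXED model with weekly repeated values, terms for week and treatment by week, and a baseline equivalent of the endpoint.

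Other parts of the documents treat abstinence differently:

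- The protocol synopsis, under analysis of the secondary endpoints, lists subjects abstinent and subjects with no heavy drinking days as dichotomous. It says their analysis "during the last 4 weeks of treatment period will be conducted via logistic regression".
- SAP 5.2.5 counts the subjects who have no drinking days in the period of interest, and counts those with no heavy drinking days in the same way.
- The second paragraph of SAP 9.4.4 begins "Covariates for the dichotomous secondary endpoints, percentage of subjects abstinent" and goes on to the two WHO endpoints.
- SAP Table 69 is a logistic-regression shell for abstinence over Weeks 3-6, with baseline percent days abstinent as covariate.

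**The concern.** For abstinence, the methods text of the SAP prescribes a different model from the protocol, from another section of the same SAP and from the output shell. A programmer working from 9.4.3.1 and one working from Table 69 would fit different models to different data structures and report different effect measures. SAP 9.1 treats a secondary p-value below 0.05 as statistically significant, and 9.4.3.1 applies no multiplicity adjustment. The choice between the two analyses should therefore not be left open until after unblinding.

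The endpoint of no heavy drinking days is first in the list of 15 secondary endpoints, yet neither of the model-assigning sentences in 9.4.3.1 names it. A reader of that section alone would not find its analysis.

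**Working it through.** The documents give no power, event rate or effect size for either endpoint, so there is no figure to reproduce. The check compares the texts.

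**Step 1: type of variable.** Under SAP 5.2.5 each subject is either abstinent over Weeks 3-6 or not. That is one 0/1 value per subject.

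**Step 2: can the 9.4.3 model take that variable?** The model is "Appropriately transformed endpoint = treatment + week + treatment\*week + clinical site + baseline equivalent of endpoint + other covariates".

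- With one value per subject, week does not vary within a subject. The week term, which has 4 − 1 = 3 degrees of freedom for Weeks 3 to 6, cannot be estimated, and neither can treatment by week.
- The choice among four within-subject covariance structures by AICc in 9.4.3 has nothing to work on.
- The transformations in SAP 9.1 do not help. The square root leaves 0 and 1 unchanged (√0 = 0, √1 = 1), and the logarithm and the inverse are undefined at 0.
- Read literally, the baseline equivalent would be baseline abstinence. The protocol requires an average of at least 28 drinks per week for men or 21 for women before consent, so this covariate would be the same for every subject.

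**Step 3: what if the endpoint is recast to fit the model?** The only way to make the model run is to score abstinence separately in each of Weeks 3, 4, 5 and 6 and treat the 0/1 score as continuous. Three things then change.

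- The endpoint changes. A subject who drinks in one of the four weeks is a failure under 5.2.5, but contributes 3 abstinent weeks of 4 (3/4 = 75%) to the weekly model.
- The effect measure changes. SAP 9.4.3 reports least squares means and Cohen's d; Table 69, which follows Table 67, reports an odds ratio with its confidence interval and Cohen's h.
- The output has no home. Table 75 is the mixed-model template for Tables 77, 79, 81, 83, 85 and 87, and none of these is for subjects abstinent.

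**Step 4: the same comparison for no heavy drinking days.**

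- SAP 9.4.3.1: not named for either model.
- SAP 9.4.4, opening list of dichotomous endpoints: not named.
- SAP 9.4.4, later in the same paragraph: baseline percent heavy drinking days is its covariate, if the number of events allows.
- SAP Table 67: full logistic shell, Weeks 3-6.
- Protocol synopsis: logistic regression.

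No passage gives this endpoint any other model. For abstinence there is a contradiction; for no heavy drinking days there is only an omission from the text.

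**The case against.** The strongest reply is that this is a drafting slip which the rest of the SAP exposes. SAP 9.4.3 confines the mixed model to continuous endpoints, 9.4.4 labels abstinence dichotomous, and the only abstinence model with a shell is logistic. A careful programmer would probably fit the logistic regression. That stands, and it limits the seriousness. It does not remove the conflict: 9.4.3.1 is the section that assigns models to the drinking endpoints, and it names the wrong one.

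It could also be said that Figure 4 plots abstinence by week, so a weekly analysis was intended. The figure is a display. It does not alter the definition in 5.2.5 or the Weeks 3-6 period in Tables 68 and 69.

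A reader might go further and infer any of the following, which the documents do not support:

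- *That no heavy drinking days has no planned analysis.* Table 67, the covariate sentence in 9.4.4 and the protocol all give it logistic regression.
- *That the two leading drinking outcomes would both give different answers.* Omitting an endpoint from a sentence assigns it no different model. The SAP also sets no testing hierarchy that would make these two the leading endpoints.
- *That Tables 66 and 68 conflict with 9.4.3.1 as well.* They are descriptive yes/no counts.
- *That a numerical gap between weekly and four-week abstinence can be stated.* It would need an assumed weekly rate and an assumed persistence between weeks, neither of which is given. It would also compare prevalences, not treatment effects.

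**Conclusion.** The point holds for abstinence. SAP 9.4.3.1 names a model that does not fit the endpoint as defined and that contradicts the protocol, SAP 9.4.4 and Table 69. For no heavy drinking days it holds only as a gap in the wording of 9.4.3.1 and of the opening list in 9.4.4.

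The conflict in method affects one of 15 secondary endpoints, and no numerical magnitude is claimed. The conclusion rests on the text alone and needs no assumption about event rates. The primary endpoint, its ANCOVA and the sample size of 60 are not touched. The correction is worth making because it is specific and nearly free, and because it settles before unblinding which analysis is reported.

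**What to change.** Three edits to the SAP text:

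1. In the first sentence of 9.4.3.1, delete subjects abstinent from the mixed-model list.
2. In the logistic-regression paragraph of 9.4.3.1, name subjects abstinent and subjects with no heavy drinking days. Suggested wording: *Abstinence from alcohol and absence of any heavy drinking day, each one yes/no value per subject over Weeks 3 through 6, will be analysed by logistic regression, with covariates as in Section 9.4.4 where the number of events allows, and reported with odds ratio, 95% CI, Cohen's h and Wald test.*
3. In the opening list of dichotomous endpoints in 9.4.4, add no heavy drinking days.

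In edit 2 the period must be written out, because the receiving paragraph defines the last four weeks as Weeks 2 through 5, whereas 9.4.3 says Weeks 3 through 6. The added endpoints must not inherit the former. That discrepancy is a separate matter, to be reconciled for the WHO endpoints too.

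The cost is a short text amendment before unblinding. Tables 66 to 69 already fit the corrected text, and no data, visits or subjects are added.
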